3.3.5. Correlative studies

Blood and marrow aspirates (and biopsies when indicated) will be obtained at diagnosis, prior to each cycle of consolidation and every 3 months during maintenance therapy.

- Monitoring MRD using WT1 transcript during consolidation and maintenance therapy with omacetaxine.
- Tissue acquisition for future studies of AML among older adults.
- In cases where a marrow was obtained at Emory to establish the AML diagnosis, prior to enrolling on the study, study marrow can be waived if sufficient circulating blasts are present in the peripheral blood.
- In cases where the presence of disseminated intravascular coagulation (DIC) due to AML places the patient at risk of bleeding, marrow collection can be waived and instead peripheral blood collection will suffice for baseline collection.

3.4. Study Drugs:

3.4.1 Omacetaxine:

[figure not shown]
Generic Name: Omacetaxine, Homoharringtonine, NSC-141633

Chemical Name: Cephalotaxine,4-methyl-2-hydroxy-2-(4-hydroxy-4-methylpentyl) butanedioate ester

Formula: C₂₉ H₃₉ N O₉

Molecular Weight: 545.6 g/mo

Structure:

Drug description:

Omacetaxine is a cephalotaxine ester alkaloid derived from the plant *Cephalotaxus fortunei*. Cephalotaxines have the empirical composition C₁₈H₂₁NO₄ and contain a methylenedioxypheno group, a secondary hydroxyl group, double bond and a vinyl methoxyl group. A variety of esters of cephalotaxine are known, and the two which have been investigated clinically are harringtonine, ester-2 and homoharringtonine, ester-3. Omacetaxine differs from harringtonine in having a methylene group inserted in the side chain. There are no known drug incompatibilities. A summary of chemistry, manufacturing, pharmacokinetics and toxicology is supplied in the Investigator's Drug Brochure.

Mechanism of action:

Omacetaxine inhibits protein synthesis and induces differentiation and apoptosis. Details are in the investigator's brochure. Kinetic studies of the effects of the agent on L-1210 cells showed a marked inhibition of thymidine incorporation, damage to tumor cells in G phase and S phase, block of the progression of cells in G2 phase into M phase and block of the traverse of the leukemic cells in G1 into S phase.

4. DATA COLLECTION:

Data will be entered onto specific case report forms, and will be managed by designated data managers and stored in the WCI database. Data will be then recorded on electronic spread sheets for statistical analyses.

5. ADVERSE EVENT REPORTING AND SAFETY MONITORING

Collection of adverse events information will be managed directly between the Study Coordinator and PI. A MedWatch Form Form will be completed for every SAE and those which meet FDA reporting requirements will be submitted to the FDA. A data and safety monitoring report will be filed with the IRB at least once per year in order to protect patients from any harm that might result from their participation in this study. See **Appendix L** for serious adverse events reporting and adverse events log.

Definition of Adverse Events (AE): An AE is defined as any untoward medical occurrence in a patient after administration of the study drug. An AE does not necessarily have a causal relationship with the use of the study drug. An AE can therefore be any unintended sign (including an abnormal laboratory finding), symptom, or disease temporally associated with the use of the study drug, whether or not related to the study drug.

Definition of Serious Adverse Events (SAE): A serious adverse event (SAE) is any medical complication that results in one of the following outcomes: death, urgent medical intervention to prevent death or disability, inpatient hospitalization for more than 24 hours or prolongation of hospitalization because of complications that could be caused by the study drugs, new persistent or significant disability or incapacity, or exacerbation of a pre-existing significant disability or incapacity.

Progression or relapse of AML are not considered AEs or SAEs and will be tracked as outcomes in the Case Report forms.

Expedited Reports of SAE's and Unexpected SAE's: The PI will immediately notify Teva Pharmaceuticals of any SAE occurring after the second registration. SAEs (during OMA consolidation/maintenance). SAEs will be sent to the Teva Pharmacovigilance safety mailbox at [contact] or [contact]. The PI will review each report to determine whether the SAE is expected or unexpected, based on information available in the study drugs label, and the study consent document approved by the IRB. An SAE will be defined as "unexpected" only if it is not listed in any of these documents and it is not expected based on the patient's medical history. The PI/ study coordinator team will notify the IRB

immediately of any deaths possibly, probably or definitely associated with the study drug or procedures, and will notify the FDA of any unexpected fatal or life-threatening event within 7 days. All unanticipated problems involving risks to participants or others (UPs) will be reported to the IRB within 10 calendar days. Death from progression of AML is not an SAE.

The Study Coordinator is responsible for filing SAE reports, patient evaluation forms, and medical records in the study file for each patient, and forwarding all SAE reports to the PI. At 3-month intervals, the Study Coordinator will prepare summaries of all AE information, compiled from SAE reports, patient questionnaires, and review of available medical records for each patient. Summary reports tabulating the occurrence of all AEs will be forwarded to the PI.

The PI is responsible for reviewing all SAE reports to determine whether the SAE is expected or unexpected. The PI is responsible for following the reporting requirements of the IRB, and the FDA. The PI is responsible for filing a semi annual or annual report to the IRB according to the IRB requirements. The PI is responsible for responding to inquiries from the IRB.

5.1 Data Safety Monitoring Plan.

Patient safety, study efficacy and compliance will be reviewed at the (Leukemia Working Group) meetings. The Data and Safety Monitoring Committee (DSMC) of the Winship Cancer Institute will provide oversight for the conduct of this study. The DSMC functions independently within Winship Cancer Institute to conduct internal monitoring functions to ensure that research being conducted by Winship Cancer Institute Investigators produces high-quality scientific data in a manner consistent with good clinical practice (GCP) and appropriate regulations that govern clinical research. Depending on the risk level of the protocol, the DSMC review may occur every 6 months or annually. For studies deemed High Risk, initial study monitoring will occur within 6 months from the date of the first subject accrued, with 2 of the first 5 subjects being reviewed. For studies deemed Moderate Risk, initial study monitoring will occur within 1 year from the date of the first subject accrued, with 2 of the first 5 subjects being reviewed. Subsequent monitoring will occur in routine intervals per the [Winship Data and Safety Monitoring Plan \(DSMP\)](#).

Data quality will be monitored on an ongoing basis by random checks of CRFs following the Leukemia Working Group meetings. Co-investigators and staff will be trained on the conduct of the protocol and any additional training based on protocol amendments at the Hematology/Leukemia multi-disciplinary meetings, which meets regularly. Recording, grading, and reporting of adverse events will be carried out contemporaneously with each patient's clinic visit and will abide by the guidelines provided by the Winship Cancer Institute Clinical Trials Office. Deviations will be added to the Deviation Log, which is updated and reviewed at the Leukemia Working Group meetings.

The Principal investigator is responsible for sending a yearly IND summary report, which includes an update and status of the study and a tabulation of the AEs/ SAEs, as well as status of the study subjects, to the FDA. The PI is also responsible for collecting, reviewing, analyzing and reporting to the FDA and other investigators any potential serious risks that qualify for reporting under the FDA's IND Safety Reporting regulations at 21 CFR §312.32, .64 and 21 CFR § 320.31. In addition, the Sponsor-Investigator must copy the Emory IRB on

any such reports and include an analysis of whether the Sponsor-Investigator believes the event constitutes an Unanticipated Problem Involving Risks to Subjects or Others.

6. STATISTICAL CONSIDERATIONS:

Safety: Target omacetaxine dose is the dose that can be delivered to 70% patients without dose limiting toxicity (DLT) as defined above (section 3.3.4). Safety analysis will be conducted through continuous monitoring of AE/SAE. If 2 of the first 3 patients experience DLT, we stop the trial. After that, we stop the trial if there is evidence that the target probability of DLT exceeds 30% and the probability of falsely stopping the trial is 10% or less. The following table gives the minimum number of DLTs in order to stop the trial and the probability of falsely terminating the trial if in fact the probability of DLT is 30% calculated using the binomial distribution. For example, if after enrolling 6 patients, 4 or more experienced DLT, then we stop the trial and conclude that the target probability of DLT is more than 30%. The probability of incorrectly stopping the trial is 0.07.

To be considered safe, the upper limit of the one-sided 95% CI of DLT among 15 patients must not be greater than 30%.

Number of Patients	3	4	5	6	7	8	9	10	11	12	13	14	15
Number of DLTs to Stop Trial	> 1	> 1	> 3	> 3	> 4	> 4	> 4	> 5	> 5	> 6	> 6	> 6	> 7
Probability of falsely terminating the trial		0.08	0.03	0.07	0.03	0.06	0.10	0.05	0.08	0.04	0.07	0.10	0.05

Feasibility: Feasibility is defined as delivery of 9 cycles of therapy for at least 2/3 of the patients. The proportion of patients with full treatment delivery will be estimated with an exact 95% confidence interval.

Futility: Based on our previous data showing a median relapse-free survival of 13.8 months, we will consider our consolidation/maintenance regimen futile if $\geq 80\%$ of those entering in CR relapse during consolidation/maintenance.

Kaplan-Meier curves will be used to estimate the distribution of time to relapse, relapse free survival, and overall survival.

Analysis of survival outcomes (OS, EFS, RFS) for patients who undergo transplantation in CR will include censoring and no censoring at the time of transplantation.

References:

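### Section 5 puts a causality qualifier inside the SAE hospitalization criterion and a medical-history test inside the definition of unexpected, so some hospitalizations may not count as SAEs and some events may miss the 7-day FDA report

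*Combined protocol and SAP*

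**What the plan says.** All the wording at issue is in Section 5 (Adverse Event Reporting and Safety Monitoring).

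- **AE.** The definition is free of causality: "An AE does not necessarily have a causal relationship with the use of the study drug".
- **SAE.** It "is any medical complication that results in one of the following outcomes: death", followed by urgent treatment to avert death or disability, a hospitalization item, and new or worsened disability. The hospitalization item names an inpatient stay longer than 24 hours and, as the alternative, "prolongation of hospitalization because of complications that could be caused by the study drugs". Threat to life is not on the list.
- **Unexpected.** The PI decides "based on information available in the study drugs label, and the study consent document approved by the IRB". An SAE is then unexpected "only if it is not listed in any of these documents and it is not expected based on the patient's medical history".
- **Reporting.** Every SAE gets a MedWatch form, and every SAE after second registration goes at once to the drug supplier. The study team informs the IRB "immediately of any deaths possibly, probably or definitely associated with the study drug or procedures". Expectedness enters in the clause on the FDA, under which the same team "will notify the FDA of any unexpected fatal or life-threatening event within 7 days". Death from AML progression is not an SAE.

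Section 5.1 adds a separate duty to report serious risks that qualify under the FDA's IND safety reporting regulations. The log in Appendix M has separate columns for seriousness and for relationship to drug, and not related is one of the relationship options.

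**The concern.** Seriousness describes what happened to the patient; relatedness is an opinion about why. The hospitalization item mixes the two, so whether a hospitalization is serious can depend on a causality judgement made before the event is reported. Two coordinators could also classify the same admission differently, because the grammar does not settle how far the qualifier reaches.

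The definition of unexpected has a similar weakness. Every treated patient has AML and recent induction chemotherapy, and Appendix G records comorbidities. A history clause with no stated limits gives the PI wide room to call an event expected, and that call controls the 7-day FDA notice.

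Safety and tolerability are the primary objectives of this open-label pilot of 15 treated patients, and Section 6 rests the safety analysis on continuous monitoring of AEs and SAEs. The SAE tabulation and the outgoing reports are what the FDA and the drug supplier will see, so the rules for entering them should be unambiguous.

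**Working it through.** The plan states no figure on this point, so the check traces which events each rule keeps in or leaves out.

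**1. Reach of the causality qualifier.** The item joins two things with *or*: a stay of more than 24 hours, and a prolonged stay. The causal phrase follows the second. On the narrow reading it limits prolongation only; on the broad reading it limits both.

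**2. Events traced through Section 5.**

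| Event, with no other serious outcome | SAE? | Consequence |
|---|---|---|
| Prolonged stay, judged not possibly drug-caused | No, on either reading | AE only: no MedWatch form, no supplier notice, absent from SAE tabulation |
| New stay over 24 h, judged likewise | Yes on the narrow reading, no on the broad | Depends on who reads the sentence |
| Life-threatening event without urgent treatment to avert death or disability and without a qualifying stay | No | The unexpected label is defined only for SAEs, so the 7-day clause names an event class that the SAE list does not fully admit |
| Fatal infection or bleed, not AML progression | Yes, through death, which has no qualifier | MedWatch and supplier notice apply; IRB at once if at least possibly related; 7-day FDA notice only if unexpected |

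**3. Logic of the unexpected label.** Two conditions are joined by *and*:

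| Listed in label or consent form? | Expected from history? | Classification |
|---|---|---|
| No | No | Unexpected |
| No | Yes | Expected |
| Yes | Either | Expected |

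The history clause changes the result only in the second row, that is, for events that neither reference document lists. For example, an unlisted cardiac event in a patient whose Appendix G score records an arrhythmia could be classed as expected. The third row has its own gap: a listed event counts as expected even if it is more severe or more specific than the listing. The Investigator's Brochure, which Section 3.4.1 cites for toxicology and Appendix J attaches, is not a reference document.

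**4. Link to the stopping rule.** Section 6 stops the trial on counts of dose-limiting toxicity (DLT) and refers to Section 3.3.4 for the definition. That section works by toxicity grade, time to recovery and attribution to omacetaxine. It uses neither SAE status nor expectedness, so an admission recorded only as an AE can still be graded and counted.

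**5. Size.** The documents give no hospitalization rate and no split by attribution, and the label and consent texts are not among them. The number of affected events therefore cannot be calculated. Only the scale is fixed: with 15 patients, each one whose only SAE is missed lowers the proportion of patients with an SAE by 1/15 = 6.7 percentage points.

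**The case against.** The case for leaving the text alone has substance. The qualifier asks only whether a complication could be drug-caused, which is a low threshold, and it is certain only for prolongation. An event that fails it is still an AE, is included in the 3-monthly summaries to the PI, and enters the yearly tabulation to the FDA. Urgent treatment to avert death covers most of what life-threatening would add, and the Appendix M log has a life-threatening grade. Section 5.1 adds the IND duty, working-group review and an independent DSMC. All of that is correct and limits the harm.

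It does not remove the defect. MedWatch forms and supplier notices begin only once an event is an SAE, so they cannot recover a hospitalization that the definition leaves out. The 3-monthly summaries go to the PI, who also makes the expectedness call. DSMC review is every 6 months or annual, with 2 of the first 5 subjects examined at initial monitoring. The IND clause sets a second test beside the Section 5 definition without saying which governs.

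Three stronger readings are tempting and unsupported:

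- *Fatal infections and bleeds drop out of the SAE counts.* They do not, because death is an unqualified SAE outcome and only death from AML progression is excluded.
- *The trial's stopping signal is biased downward.* The DLT rule does not use SAE status.
- *The PI must screen events with the Section 5 definitions before the IND duty applies.* No text sets that order.

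**Conclusion.** The point holds as a defect in the reporting definitions, and it should be corrected because safety is the primary objective. Three parts stand:

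- Prolonged stays judged unrelated, and possibly initial admissions, can be left out of the SAE data.
- Life-threatening events trigger a 7-day report but are only partly covered by the SAE outcomes.
- An event absent from both label and consent form can be called expected from history and miss the 7-day report, which leaves a standard at odds with the separate IND duty.

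The effect is confined to SAE classification and expedited reporting; AE records, deaths as SAEs, immediate IRB notice of possibly related deaths and the DLT rule are untouched. Its size is unknown. A reader might infer that most serious events in these patients would be lost, but nothing in the documents supports any such share. The conclusion rests on the wording alone and assumes that staff apply Section 5 as written.

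**What to change.** Reword Section 5:

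1. Define an SAE by outcome only. Delete the causality phrase from the hospitalization item and add life-threatening to the listed outcomes.
2. Record relatedness separately, in the column that the Appendix M log already has.
3. Define unexpected against named reference documents, the label and the Investigator's Brochure, and state that an event of greater severity or specificity than listed is unexpected.
4. Delete the medical-history clause. A patient's history belongs in the causality assessment.
5. Keep the exclusion of AML progression and relapse as it stands.

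The cost is a wording change in one section, a few more SAE and MedWatch forms in about 15 patients, and a slightly higher reported SAE rate. No change to sample size, stopping boundaries or visit schedule is needed.

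### DLT stopping table, n=4: the boundary `> 1` has a false-stop probability of 0.35, not the printed 0.08, which breaks the plan's 10% limit and leaves its 6-patient example unable to add a stop

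*Combined protocol and SAP*

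**What the plan says.** Section 6, Statistical Considerations (Safety), sets two layers of stopping. The first is "If 2 of the first 3 patients experience DLT, we stop the trial". From then on the trial stops on evidence that the DLT rate exceeds 30%, provided "the probability of falsely stopping the trial is 10% or less".

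The accompanying table covers 3 to 15 patients. Its row "Number of DLTs to Stop Trial" reads `> 1` at both n=3 and n=4, then `> 3` at n=5 and n=6, rising to `> 7` at n=15. Its row "Probability of falsely terminating the trial" is blank at n=3 and reads 0.08 at n=4, 0.03 at n=5 and 0.07 at n=6. The text says these are tail probabilities "if in fact the probability of DLT is 30% calculated using the binomial distribution".

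A worked example fixes the notation: "if after enrolling 6 patients, 4 or more experienced DLT, then we stop the trial", and "The probability of incorrectly stopping the trial is 0.07". So `> 3` means 4 or more, and `> 1` at n=4 means 2 or more.

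**The concern.** The two n=4 cells look incompatible: 2 or more DLTs in 4 patients is a common outcome at a 30% rate, so 0.08 is far too small. The boundary is also out of step with the next column, because 2 DLTs in 4 stops the trial while 3 in 5 does not.

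This is a live threshold for the primary safety objective in a 15-patient study. As printed, one DLT among the first three patients and one in the fourth ends the trial with the conclusion that the DLT rate exceeds 30%. A reader who relies on the printed probability, the 10% limit or the worked example would continue. Two people applying the same protocol at 2 of 4 could reach opposite decisions.

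**Working it through.** **Inputs (all from Section 6, Safety).** Null DLT rate p = 0.30; limit 0.10 on false stopping after the n=3 rule; binomial calculation; boundaries and probabilities as printed.

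**Step 1. Reproduce the plan's own figure.** For a boundary `> k` at n patients, the per-look probability is P(X ≥ k+1), X ~ Binomial(n, 0.30). At n=6, `> 3`: P(X ≥ 4) = 0.0705. The plan states 0.07, so the convention is confirmed.

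**Step 2. Apply it to every column.**

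| n | Boundary | Exact | Printed |
|---|---|---|---|
| 3 | `> 1` | 0.216 | blank |
| 4 | `> 1` | **0.348** | **0.08** |
| 5 | `> 3` | 0.031 | 0.03 |
| 6 | `> 3` | 0.071 | 0.07 |
| 7 | `> 4` | 0.029 | 0.03 |
| 8 | `> 4` | 0.058 | 0.06 |
| 9 | `> 4` | 0.099 | 0.10 |
| 10 | `> 5` | 0.047 | 0.05 |
| 11 | `> 5` | 0.078 | 0.08 |
| 12 | `> 6` | 0.039 | 0.04 |
| 13 | `> 6` | 0.062 | 0.07 |
| 14 | `> 6` | 0.093 | 0.10 |
| 15 | `> 7` | 0.050 | 0.05 |

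Only n=4 is materially wrong. By hand: P(X ≥ 2 of 4) = 1 − 0.7⁴ − 4(0.3)(0.7³) = 1 − 0.2401 − 0.4116 = 0.3483. For `> 2`: 4(0.3³)(0.7) + 0.3⁴ = 0.0756 + 0.0081 = 0.0837, which rounds to the printed 0.08.

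**Step 3. Try other readings of `> 1` at n=4.** Reading it as 1 or more gives 0.760. The chance of stopping for the first time at n=4 (exactly 1 DLT in 3, then a DLT) is 0.441 × 0.3 = 0.132. Conditional on passing n=3, that is 0.132/0.784 = 0.169. None is 0.08 and all exceed 0.10.

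**Step 4. Find the rule behind the table.** The smallest boundary with a tail of 0.10 or less reproduces all 11 printed boundaries from n=5 to n=15. At n=4 the same rule gives `> 2`.

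**Step 5. Check which looks can act.** A trial that continues past n=4 as printed has at most 1 DLT. The most it can then have is 2 at n=5, 3 at n=6 and 4 at n=7, against 4, 4 and 5 needed to stop. None of these looks can trigger. With `> 2` at n=4, the path 1 of 3, 2 of 4, 3 of 5, 4 of 6 is open.

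**Step 6. Sequential false stopping at p = 0.30.** The recursion goes patient by patient, removing stopped trials at each n from 3 to 15.

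| Stop at | As printed | n=4 set to `> 2` |
|---|---|---|
| n=3 | 0.216 | 0.216 |
| n=4 | 0.132 | 0 |
| n=5 | 0 | 0 |
| n=6 | 0 | 0.012 |
| n=7 to 15 | 0.031 | 0.053 |
| After n=3 | 0.163 | 0.065 |
| After n=3, given n=3 passed (÷ 0.784) | 0.208 | 0.083 |
| Overall | 0.379 | 0.281 |

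Overall stopping at other true DLT rates, as printed versus `> 2`: 0.186 vs 0.117 at 20%; 0.602 vs 0.513 at 40%; 0.803 vs 0.749 at 50%.

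**The case against.** Several points can be made for the plan.

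- **The 0.35 overstates the harm of the n=4 look itself.** Of the 0.348, 0.216 has already been stopped by the 2-of-3 rule, and the n=4 look adds 0.132. This is right as a statement of incremental effect. But 0.348 is the like-for-like value of the printed cell, since every other cell is the same kind of per-look tail, and 0.132 also exceeds 10%.
- **A trial with 2 DLTs in 4 could not have been declared safe anyway.** The end-of-trial criterion requires a one-sided 95% upper limit of at most 30% among 15 patients. If an exact limit is assumed (the plan names no method), 1 of 15 gives 0.279 and 2 of 15 gives 0.363, so at most 1 DLT qualifies. This lowers the stakes for the final safety claim. It does not restore the feasibility and secondary data lost by stopping at patient 4, nor support the conclusion that the rate exceeds 30%.
- **The printed boundary errs towards earlier stopping.** True, and moving to `> 2` has a price at high DLT rates, shown above.
- **Irregularities remain with `> 2`.** Two DLTs in 3 would still stop the trial while 2 in 4 would not, and the looks at n=4, 5, 7, 10, 12 and 15 could never trigger. So the comparison with neighbouring columns does not by itself identify the n=4 boundary as the slip; the match to 0.08 and to the 10% rule is the stronger evidence. A deliberate carry-over of the n=3 rule, or a digit misread when the PDF was converted, cannot be excluded.
- **Overlapping enrolment could let 4 of 6 be observed.** Section 3.3.4 judges toxicity over windows of 36 to more than 50 days, so DLTs may be learned late. But patients 5 and 6 contribute at most 2 DLTs, so any 4 of 6 includes at least 2 among the first 4. If the boundaries apply to the first n patients, the n=6 boundary still adds no stop.

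**Conclusion.** The concern holds. The n=4 boundary and its printed probability cannot both be right: 0.348 against 0.08. The boundary as printed breaks the plan's 10% limit, which exempts only the n=3 rule, and it empties the worked example. At a 30% DLT rate it raises false stopping after the third patient from 0.065 to 0.163, and overall from 0.281 to 0.379.

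The contradiction needs no assumption beyond the plan's own inputs. The sequential figures assume independent patients, DLT status known before the next look, and boundaries applied in order to the first n patients. Which cell is the slip is likely (the boundary) but not proved. The blank n=3 cell, the missing per-look label and the rounding at n=13 and n=14 are minor and change no boundary.

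**What to change.** The sponsor should reconcile four items in Section 6: the n=4 boundary, its probability, the 10% limit and the 6-patient example.

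- `> 2` is the entry consistent with the printed 0.08 and with the rule that generates n=5 to n=15. The n=4 look then cannot trigger after the 2-of-3 rule, and the example becomes reachable.
- If `> 1` is intended, the probability should read 0.35, the text should place n=4 outside the 10% limit, and the example should be replaced.

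In either case, enter 0.22 at n=3, label the row as per-look probabilities, and correct n=13 and n=14 to 0.06 and 0.09. State the overall false-stop probability at a 30% DLT rate including the 2-of-3 rule (0.38 as printed, 0.28 with `> 2`), so that 10% is not taken for the overall rate.

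The cost is one table and a few sentences, with no extra patients, and a less favourable stated error rate. If the boundary is the entry changed, the trial stops less often when DLT is truly high: 0.75 instead of 0.80 at a 50% rate, and 0.51 instead of 0.60 at 40%.

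### The DLT stopping table gives single-look probabilities as the chance of falsely terminating the trial; over the whole rule that chance is about 0.28 at a 30% DLT rate, mostly from the 2-of-3 rule, whose cell is blank

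*Combined protocol and SAP*

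**What the plan says.** All of this is in section 6, Statistical Considerations, under Safety, and in the table there.

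- Monitoring: "Safety analysis will be conducted through continuous monitoring of AE/SAE".
- First rule: "If 2 of the first 3 patients experience DLT, we stop the trial".
- Later looks: the next sentence applies from that point on. It stops the trial when there is evidence of a DLT rate above 30% and "the probability of falsely stopping the trial is 10% or less".
- The table is introduced as giving the minimum number of DLTs for stopping and "the probability of falsely terminating the trial if in fact the probability of DLT is 30% calculated using the binomial distribution".
- The row "Number of DLTs to Stop Trial" has a boundary at each n from 3 to 15.
- The row "Probability of falsely terminating the trial" has a value for each n from 4 to 15, between 0.03 and 0.10. The n=3 cell is blank.
- Worked example, 4 or more DLTs in 6 patients: "The probability of incorrectly stopping the trial is 0.07". The text then concludes that the DLT probability is above 30%.

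The section gives no stopping probability for the rule as a whole, and does not say that the tabulated values refer to one look in isolation.

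**The concern.** A binomial tail at n=6 is the chance of seeing 4 or more DLTs if the data are examined once, at six patients. The trial is not run that way. It can stop at any n from 3 to 15, so its chance of stopping falsely is the chance of crossing at least one boundary. The row label and the n=6 example nevertheless describe the trial as a whole.

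Safety and tolerability are the primary objectives, and section 1.6 presents the pilot as a step towards a phase II efficacy trial. If the trial stops, investigators and the monitoring committee will read the stop as evidence against the regimen. The table tells them that this conclusion carries an error of 3 to 10%. They should know the error of the rule actually applied.

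**Working it through.** **Inputs (section 6).** DLT rate for a false stop: p = 0.30. Maximum 15 patients. Boundaries, stop if DLTs exceed: n=3: 1; 4: 1; 5: 3; 6: 3; 7: 4; 8: 4; 9: 4; 10: 5; 11: 5; 12: 6; 13: 6; 14: 6; 15: 7.

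**Step 1: reproduce the printed row.** With boundary b, the single-look tail is P(X > b), X ~ Binomial(n, 0.30). The cumulative columns are from step 2.

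| n | Stop if | Printed | Single-look tail | Cumulative, > 2 at n=4 | Cumulative, > 1 at n=4 |
|---|---|---|---|---|---|
| 3 | > 1 | blank | 0.216 | 0.216 | 0.216 |
| 4 | > 1 | 0.08 | 0.348 (> 2: 0.084) | 0.216 | 0.348 |
| 5 | > 3 | 0.03 | 0.031 | 0.216 | 0.348 |
| 6 | > 3 | 0.07 | 0.071 | 0.228 | 0.348 |
| 7 | > 4 | 0.03 | 0.029 | 0.228 | 0.348 |
| 8 | > 4 | 0.06 | 0.058 | 0.236 | 0.352 |
| 9 | > 4 | 0.10 | 0.099 | 0.255 | 0.362 |
| 10 | > 5 | 0.05 | 0.047 | 0.255 | 0.362 |
| 11 | > 5 | 0.08 | 0.078 | 0.264 | 0.367 |
| 12 | > 6 | 0.04 | 0.039 | 0.264 | 0.367 |
| 13 | > 6 | 0.07 | 0.062 | 0.269 | 0.371 |
| 14 | > 6 | 0.10 | 0.093 | 0.281 | 0.379 |
| 15 | > 7 | 0.05 | 0.050 | 0.281 | 0.379 |

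From n=5 the printed values are the single-look tails to within 0.01; n=13 and n=14 are printed slightly high. At n=4 the printed 0.08 fits > 2, not the printed > 1.

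**Step 2: the rule as run.** Carry the distribution of the DLT count forward one patient at a time, and remove the paths that meet the boundary at each n from 3 to 15. The removed probability is the cumulative chance of stopping. The first terms can be checked by hand:

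- n=3: 3 × 0.3² × 0.7 + 0.3³ = 0.189 + 0.027 = 0.216.
- n=4 with > 2: a continuing trial has at most 1 DLT in 3, so it cannot reach 3 in 4. Adds 0.
- n=4 with > 1: exactly 1 DLT in 3 has probability 3 × 0.3 × 0.7² = 0.441. Adds 0.441 × 0.3 = 0.132, giving 0.348.
- n=6 with > 2 at n=4: needs 1 DLT in the first 3 and then 3 in a row. Adds 0.441 × 0.3³ = 0.012, giving 0.228.

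**Step 3: split at the first three patients.** The chance of passing n=3 is 1 − 0.216 = 0.784.

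- > 2 at n=4: later looks add 0.281 − 0.216 = 0.065, or 0.065 / 0.784 = 0.083 among trials that pass n=3.
- > 1 at n=4: later looks add 0.379 − 0.216 = 0.163, or 0.163 / 0.784 = 0.208 among trials that pass n=3.

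**Step 4: whole-rule stopping probability at other true DLT rates.**

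| True DLT rate | 10% | 20% | 30% | 40% | 50% |
|---|---|---|---|---|---|
| > 2 at n=4 | 0.03 | 0.12 | 0.28 | 0.51 | 0.75 |
| > 1 at n=4 | 0.05 | 0.19 | 0.38 | 0.60 | 0.80 |

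At 20% the 2-of-3 rule alone gives 3 × 0.2² × 0.8 + 0.2³ = 0.104, most of the 0.12.

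**Step 5: fewer looks.** With looks only at n = 3, 6, 9, 12 and 15, the figure at 30% is 0.265.

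**The case against.** The 10% sentence follows the 2-of-3 rule and is tied to what comes after it. No probability is printed for n=3, so the plan claims no 10% there. With that rule in force and > 2 at n=4, all later looks together add 0.065, or 0.083 among trials that pass n=3. Both are under 10%. From n=5 each boundary is also the smallest count whose single-look tail is at most 0.10, so the sentence records how the boundaries were chosen. A cautious rule is reasonable in a 15-patient pilot, and the final safety declaration uses a separate confidence-limit criterion.

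All of that stands, and it rules out some stronger readings. A reader might infer that the plan promises 10% for the whole trial including the first three patients; the order of the sentences does not support that. A reader might drop the n=3 look, obtain 0.183 for the remaining boundaries with > 2 at n=4, and conclude that the later looks break the limit by themselves. That calculation describes a design without the 2-of-3 rule: it lets trials continue that this protocol would already have stopped. A reader might also take 0.38 as the effect of repeated looks, but that figure depends on an n=4 cell that contradicts its own probability.

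The objection does not reach the row label or the n=6 example. Both are worded as the chance of wrongly stopping the trial, and the numbers beside them are neither that chance nor the conditional chance after n=3.

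**Conclusion.** The table and the worked example are wrong as labelled. They show single-look tails of 0.03 to 0.10 as trial-level false-stop probabilities, while the whole rule stops with probability 0.281 at a true DLT rate of 30%, taking > 2 at n=4. About three quarters of that (0.216 / 0.281 = 0.77) comes from the first rule, whose probability is not given. The 10% limit can be defended only for looks after the first three patients, and cumulatively over those looks only with > 2 at n=4. If the printed > 1 is applied, the whole rule gives 0.379 and the later looks exceed 10%.

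The figures assume a look after every patient from n=3 to n=15, independent DLTs with a common rate, and each patient's DLT status known at each look. Delayed ascertainment would change them somewhat; the five-look schedule still gives 0.265. The finding concerns the stated error rate and does not show that the boundaries are unsuitable.

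**What to change.** In section 6, Safety:

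1. Relabel the probability row, and reword the n=6 example, as the probability of crossing the boundary at that single look when the DLT rate is 30%.
2. Enter 0.22 in the blank n=3 cell.
3. Keep the 10% sentence, but say that it applies to each look after the first three patients and not to the trial as a whole.
4. Reconcile the n=4 boundary with its printed probability: > 1 and 0.08 cannot both stand.
5. Add the cumulative stopping probability of the whole rule at true DLT rates of 10, 20, 30, 40 and 50%, using the row of step 4 that matches the reconciled n=4 boundary, and state the assumption about when DLT status is known.

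Apart from the n=4 cell, the boundaries may stay as they are. The cost is a few lines of text and a less favourable stated error rate.
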